2.3 Risk and Benefit Assessment

2.3.1 Potential Risks

The only known study-related risk is the use of a nasal cannula to deliver cold air to the participant. The potential risks associated with this delivery are:

Nosebleed

Shivering

Irritation of the nasal passages

Skin irritation at the site of the cannula

Nasal congestion

Over cooling

Participants will be de-identified using a study specific number at the time of enrollment. All Case Report Forms (CRFs) will be labeled with the de-identified participant identification (ID) number. No identifiable participant identification information will be provided to NeuroIntact.

Information collected for this study is confidential. However, officials of the Food and Drug Administration (FDA) or other regulatory agencies may research records during the ordinary course of carrying out their functions. A Sponsor representative may also inspect the research records to make certain the study data is accurate. The Investigator, regulatory agencies, and the Sponsor will protect the confidentiality of the records.

2.3.2 *Risk Mitigation*

The protocol has been designed to minimize the risks to study participants enrolled in the study. In general:

- Prior to study enrollment the Investigator must ensure the participant meets the inclusion/exclusion criteria
- Each participant will be fully informed about the conditions of study participation, and the risks and potential benefits of the study procedure and asked to provide an executed Informed Consent prior to being enrolled in the study
- Institutional Review Board (IRB) review and approval of the study protocol, Informed Consent Form, and any other participant-facing documents will be obtained prior to study initiation.
- The participant's core temperature will be continuously monitored with direction to adjust the VCool if the core temperature is $<35^{\circ}\text{C}$ for a sustained period of 5 minutes, to mitigate overcooling of the participant
- If the participant develops a nosebleed, the VCool will be stopped
- Participants will be assessed for shivering and if severe according to the Bedside Shivering Assessment Scale, the VCool flow and temperature will be adjusted

2.3.3 *Potential Benefits*

The information obtained in this study will not benefit the study participants directly but may aid future patients requiring cooling of body temperature.

2.4 *Study Rationale*

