2. If temperature continues to fall below 35°C after 2 minutes, cover patient with electric blanket that has been pre heated on standby. Keep blanket on until temperature gets back to 35°C.

Assess for shivering every 10 minutes using the BSAS. Record the results and time. The BSAS is recorded throughout the study.

Bedside Shivering Assessment Scale

0	None
1	Mild: Shivering localized to neck/thorax
2	Moderate: Intermittent involvement of the upper extremities and/or thorax
3	Severe: Generalized shivering or sustained upper and/or lower extremity shivering

The flow can be increased to 40 liters per minute after 10 minutes

Record any VCool System adjustments to flow rate or temperature and record the new flow rate and temperature and time of adjustment. Record the reason for the adjustment.

Assess the participant for adverse events (AEs) throughout the study

If the participant has a nosebleed, discontinue the study and note the time.

Monitor patient at first sign of shivering

- If **Mild**, cover patient with regular blanket.
- If **Moderate or severe** – discontinue cooling treatment.

Continue to record the temperature until either temperature sensor reaches 35.5°C or the VCool System has been used for 2 hours. Note the time the target temperature was achieved.

If the participant's core body temperature does not reach 35.5°C in 2 hours, the study is concluded

- Remove the nasal cannula from the participant and dispose of it properly
- Monitor the participant's core body temperature until it returns to baseline. Blankets can be applied to help with warming.
- Remove the axillary thermometer

If the participant's core body temperature reaches 35.5°C, proceed to the next steps

Maintain the target temperature of 35.0°C to 36.0°C for 1 hour:

Adjust flow rate by 5 liters per minute from baseline every 2 minutes

- If temperature falls below 35°C., reduce flow rate by 5 liters per minute every 2 minutes until temperature rises back to 35°C
- If temperature rises above 36°C, increase flowrate 5 liters per minute every 2 minutes until temp falls below 36°C

Remove the nasal cannula and the air delivery tube and dispose of them properly

Once out of the MRI suite, record the patient temperature (°C) using the 3M SpotOn® zero-heat-flux forehead sensor, the Braun ThermoScan 7 tympanic sensor

Monitor the participant's core body temperature until it returns to baseline. Blankets can be applied to help with warming.

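### Exit forehead and tympanic readings are written only for participants who reach target and go through the hold; non-reachers have none, and early stops have no explicit post-cooling steps

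*Protocol*

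**What the plan says.** **Baseline.** Section 7.5 has temperature read on three devices (forehead, tympanic and an MRI-compatible axillary sensor) and then takes the forehead and tympanic sensors off before the scan.

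**During cooling.** Section 7.6.3 sets the recording rule: "Continue to record the temperature until either temperature sensor reaches 35.5°C or the VCool System has been used for 2 hours". It then splits into two branches.

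- Target missed: "If the participant's core body temperature does not reach 35.5°C in 2 hours, the study is concluded". The bullets under this cover cannula removal, watching core temperature back to its starting value, and taking off the axillary thermometer.
- Target met: "If the participant's core body temperature reaches 35.5°C, proceed to the next steps". These steps are the maintenance hour, removal of cannula and tube, the exit reading ("Once out of the MRI suite, record the patient temperature", by forehead and tympanic sensor), and watching temperature back to its starting value.

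**Early stops.** For a nosebleed, Section 7.6.3 says "If the participant has a nosebleed, discontinue the study and note the time". For moderate or severe shivering it says "discontinue cooling treatment". Neither instruction is followed by post-cooling steps. Section 8 asks only that the main reason for discontinuation go on the CRF.

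**Risk mitigation.** Section 2.3.2 words both events differently. For a nosebleed: "If the participant develops a nosebleed, the VCool will be stopped". For shivering: "if severe according to the Bedside Shivering Assessment Scale, the VCool flow and temperature will be adjusted".

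**The concern.** The forehead and tympanic sensors are off during the scan, so the exit reading is the only chance to compare them with baseline. If that reading is tied to success on the primary endpoint, it is missing where it would be most useful. A participant recorded as never reaching 35.5°C may truly not have cooled, or the axillary sensor may not have followed a real fall. A second reading on the way out would help to tell these apart. The first primary endpoint is whether 35.5°C is reached within 2 hours, so this bears on how a failure is interpreted.

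The second matter is early stops. Nosebleed and shivering are among the events this feasibility study should describe well. The protocol does not say explicitly what is observed and recorded after cooling ends for either, and its two sections on these events do not use the same words.

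**Working it through.** The protocol gives no figure to reproduce here. The check sets its instructions side by side.

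**Step 1. What is written for each way cooling can end (Sections 7.6.3 and 8)**

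| How cooling ends | Observation back to baseline | Exit forehead and tympanic reading |
|---|---|---|
| Target reached, hold completed | Written | Written |
| Target not reached in 2 hours | Written | Not written |
| Nosebleed | Not written | Not written |
| Moderate or severe shivering | Not written | Not written |

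The exit reading appears in one row of four.

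**Step 2. What this means for the paired data.** Let n be the number started on VCool and r the number who reach target and go through the hold. As written, the number of baseline/exit pairs is at most r, and the remaining n − r participants supply none. The protocol gives no expected r. As an illustration only, with n = 10 and r = 6 there are 6 pairs and 10 − 6 = 4 participants without one. Over the possible range, r = 10 leaves nobody without a pair and r = 0 leaves all 10. Whatever r is, no pair comes from a non-reacher. The true n cannot be fixed either: Section 7.3.1 keeps screening until 10 have completed, and completion is not defined, so n may exceed 10.

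**Step 3. How far below baseline an early stop could be.** Section 6.1 admits core temperatures of 36.8 to 37.5°C, and the target is 35.5°C.

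- 36.8 − 35.5 = 1.3°C
- 37.5 − 35.5 = 2.0°C

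A participant stopped just short of target could therefore be nearly 1.3 to 2.0°C below the starting value. This is a ceiling for stops before target, not a forecast.

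**Step 4. Does other text fill the gap?**

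- Section 7.6.3 has temperature, BSAS and adverse events followed for the whole study. After a shivering stop, where only cooling ends, these clauses still apply. After a nosebleed, where the study itself is discontinued, it is unclear whether they do.
- Section 10 records adverse events to the end of the study visits, and Section 14 follows unresolved ones for 24 hours. Neither calls for a temperature. Section 6.3 says no follow-up is required.
- None of these clauses asks for the forehead or tympanic exit reading.

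**Step 5. The two sections on early stopping**

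| Event | Section 2.3.2 | Section 7.6.3 |
|---|---|---|
| Nosebleed | Device stopped | Study discontinued, time noted |
| Severe shivering | Flow and temperature adjusted | Cooling discontinued |

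The nosebleed entries differ in scope and can both be followed. The severe-shivering entries cannot: the device is either adjusted and kept running, or cooling ends.

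**The case against.** Several stronger readings are tempting, and the document does not support them.

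- **That early-stopped participants leave without rewarming or temperature data.** The protocol never says so; this would be an inference from silence. In the missed-target branch the study is declared over and temperature is still followed back to baseline, so ending the study does not necessarily end observation in this document. An early stop might also be read into that branch, although its condition is worded around the full 2 hours.
- **That nothing is observed after a shivering stop.** Only cooling ends, so the whole-study monitoring clauses continue. Read literally, the recording rule also continues for someone who has met neither of its end conditions.
- **That the nosebleed wordings contradict each other.** Discontinuing the study includes stopping the device. What is unclear is whether observation goes on.
- **That a before/after result will be biased.** Neither Section 5 nor Section 12.1 plans a before/after forehead or tympanic analysis. What is lost is a check on the axillary reading, not the validity of a stated analysis.

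It can also be argued that the closing steps in Section 7.6.3 are not bulleted under a condition and so apply to everyone, the more so as layout may have been lost in the PDF. That is possible. Against it, the missed-target branch has its own closing list, and two of that list's items recur after the hold, which would be redundant if the later block were common to all. The missing exit reading also remains if early stops are read into the missed-target branch, because that list does not contain it.

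**Conclusion.** The point holds as a gap in data collection plus two wordings to reconcile. As written, paired forehead and tympanic readings come only from participants who reached target, so they cannot check the axillary reading in non-reachers. No explicit post-cooling steps exist for a nosebleed or shivering stop, and Section 8 supplies none. General monitoring and the 24-hour adverse-event follow-up cover part of this, more clearly after shivering than after a nosebleed.

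The size is zero pairs from non-reachers, whatever their number, and a possible shortfall of nearly 1.3 to 2.0°C at an early stop with no explicit requirement to observe the return to baseline. The conclusion assumes that the closing block belongs to the target-reached branch and that the axillary sensor is the body sensor read in the scanner. Section 7.6.3 speaks of two sensors there, but Section 7.5 leaves only the axillary one in place. It is worth correcting before enrolment because the change is cheap and, with about 10 participants, each missing pair counts.

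**What to change.** 1. In Section 7.6.3, move the existing exit forehead and tympanic reading into one end-of-cooling data-collection step for every participant started on VCool, unless consent is withdrawn.
2. At any early stop, record the temperature and the elapsed cooling time as well as the clock time.
3. Have the sponsor and investigator reconcile Sections 2.3.2 and 7.6.3 on the nosebleed action (device stopped or study discontinued) and on severe shivering (settings adjusted or cooling discontinued), and state which of the existing post-cooling observations apply after each stop. No clinical rule is proposed here.

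The cost is a rearrangement of text in Section 7.6.3, a matching CRF change, and a few extra minutes on site for participants who stop early or miss target. The sensors and staff are those already in use.

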4 INVESTIGATIONAL PLAN

4.1 Study Design

This is a single-center, prospective, open label, feasibility study in healthy adult participants. Eligible participants who have signed an informed consent will be enrolled in the study. The participant will be assigned a unique ID number. After obtaining relevant demographic information, testing will ensue.

Baseline vital sign measurement (heart rate, temperature, blood pressure, respiratory rate) will be obtained. The participant will then undergo continuous MRI of the brain to include sequences that enable thermography. Baseline imaging sequences will take approximately 30 minutes. The investigator or designee will turn on the VCool System, while the VCool remains outside of the MRI suite, for up to two hours or until the target temperature of 35.5°C is reached. Body temperature will be continuously measured using a MRI compatible thermometer. During the cooling period and once endpoint is reached the participant will undergo repeated MRI with thermography. Once study endpoint is reached, the participant will be taken off of VCool and MRI thermography. If the target core body temperature is reached before 2 hours, the participant will be monitored until two hours are completed to determine if the VCool System can maintain the participant's core body temperature between 35°C and 36°C for one hour.

During the study, the participants will have their temperature monitored and will be assessed for shivering and adverse events.

Study participation is one visit lasting approximately 4 hours.

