7.5 Baseline Data

The following demographic information will be obtained and documented on the CRF for all enrolled participants:

Age

Sex

Race

Ethnicity

Height (inches)

Weight (pounds)

Wipe the lateral forehead with an alcohol wipe. Place the 3M SpotOn® zero-heat-flux temperature sensor on the participant's forehead.

Record the patient temperature (°C) using the 3M SpotOn® zero-heat-flux forehead sensor, the Braun ThermoScan 7 tympanic sensor, and an MRI compatible axillary sensor.

Remove the 3M SpotOn® zero-heat-flux forehead sensor and the Braun ThermoScan 7 tympanic sensor before escorting to MRI suite.

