7.6 Procedure

7.6.1 **VCool System Set Up**

Attach the disposable delivery tube to the VCool System

Install the gas inlet filter on the back with the filter bowl vertical (glass side down)

Attach the air hose to the gas inlet filter

Connect the power cord to a grounded outlet

Turn the power switch to "ON"

Connect the RS232 cable to the VCool System and to the laptop computer

Turn on the computer

Select the following:

TC-48-20 program.

COM5

Communications

Set Point and set value to -19.0

Controller options

Save data to file

Go to file Explorer, select LabView Data

Select New and enter participant identification number as file name

Save data to file

Turn on gas and set flow meter to 35 liters per minute.

Confirm temperature is set to -10°C

Confirm gas temperature setting at the end of the delivery tube is -5°C

Attach nasal cannula to the delivery tube

7.6.2 *MR Imaging procedure*

- Participants will undergo MRI at the HSF3 research facility at the University of Maryland, Baltimore (UIMB). Each imaging session will last approximately 90 minutes. The protocol will include high-resolution anatomical MRI for structural reference and tissue segmentation; MR Spectroscopy (MRS) to measure metabolite and water resonance frequencies for temperature estimation; MR Thermometry to measure phase changes over time to track temperature dynamics; Perfusion MRI to measure cerebral blood flow (CBF); as well as other structural and functional imaging sequences. These sequences will be repeated at multiple time points during the controlled cooling period to monitor temporal changes in temperature, perfusion, and tissue properties.

7.6.3 *Participant Set Up and Monitoring*

Have the participant lie on their back in an inclined position and place the nasal cannula on the participant, securing the straps around their head

Record the temperature from both temperature sensors and record the time

Record the flow rate

Initiate the cooling and record the time. The induction phase for participant cooling can take up to 2 hours.

Record the core body temperature every 2 minutes from both temperature sensors and record the time. The core body temperature is monitored throughout the study.

If the core body temperature is <35°C for 5 minutes:

1. Remove nasal cannula, if temperature starts to rise after 2 minutes keep cannula off until temperature gets back to 35°C. Then reapply nasal cannula and resume treatment.

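### Primary endpoints are stated on core temperature, but section 7.6.3 times the target on *either* of two sensors when only an axillary sensor, never designated as core, remains during cooling

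*Protocol*

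**What the plan says.** **Before the scanner.** Protocol section 7.5 takes three baseline readings: a zero-heat-flux forehead sensor, a tympanic sensor and an MRI compatible axillary sensor. It then instructs: "Remove the 3M SpotOn® zero-heat-flux forehead sensor and the Braun ThermoScan 7 tympanic sensor before escorting to MRI suite".

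**During cooling.** Section 4.1 places cooling alongside MRI and says: "Body temperature will be continuously measured using a MRI compatible thermometer". Section 7.6.3 has a pre-cooling step, "Record the temperature from both temperature sensors and record the time", and then "Record the core body temperature every 2 minutes from both temperature sensors and record the time". The target step reads "Continue to record the temperature until either temperature sensor reaches 35.5°C or the VCool System has been used for 2 hours", after which the time of reaching target is noted.

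**Afterwards.** If the target is not reached, the closing steps of 7.6.3 include "Remove the axillary thermometer". If it is reached, the other two sensors come back only outside the suite: "Once out of the MRI suite, record the patient temperature (°C) using the 3M SpotOn® zero-heat-flux forehead sensor", together with the tympanic sensor. The instruction to remove these two sensors before going to the suite then appears a second time, after the post-scan readings.

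**What depends on the reading.** Section 5.1 states all three primary endpoints on core body temperature: 35.5°C within 2 hours, a brain–core gradient, and 35–36°C for one hour. The Synopsis and section 6.1 set entry at a core temperature of 36.8–37.5°C. Section 12.1 calculates time and flow rate to 35.5°C from a measured baseline and counts the participants who reach target. Section 12.4 describes how brain temperature is derived and is silent on the body side.

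**The concern.** The target sentence in 7.6.3 is the only target rule that refers to sensors, and it presupposes two of them where the stated procedure leaves one. Once the surplus wording is set aside, an axillary reading carries every primary endpoint under the label of core temperature, without any section having designated it so.

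Two things are at stake. The first is what the trial can conclude: a result measured at the axilla would be reported as a core result. The second is comparability. If the sensor used for entry or baseline differs from the one used at target, a calculated fall mixes a between-sensor difference with the effect of the device. Section 2.2 intends to use the cooling response to build cooling models and the control algorithm, so this reaches beyond the count.

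**Working it through.** The plan gives no figure to reproduce here. The check is a sensor count, followed by arithmetic for scale.

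**1. Sensors available at each stage**

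| Stage | Source | Sensors available | Sensors the text calls for |
|---|---|---|---|
| Baseline | 7.5 | forehead, tympanic, axillary (3) | all three |
| Just before cooling | 7.6.3 | 3 − 2 = 1 (axillary) | both |
| Cooling, every 2 minutes | 4.1, 7.6.3 | 1 (axillary) | both |
| Reaching 35.5°C | 7.6.3 | 1 (axillary) | either |
| Outside the suite | 7.6.3 | forehead and tympanic named | those two |

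MR thermometry cannot be the missing second sensor. Section 12.4 derives brain temperature from it, whereas the 2-minute step asks for core body temperature from each sensor.

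**2. Is a core sensor named?**

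- Entry range (Synopsis, 6.1): no, and three readings exist.
- Baseline in 12.1: no. At least four readings could serve: three in 7.5 plus the pre-cooling reading in 7.6.3 (3 + 1 = 4).
- Endpoint 1: only by elimination (axillary).
- Endpoint 2, body side of the gradient: no.
- Endpoint 3, one-hour maintenance: no. As the steps of 7.6.3 are ordered, this hour precedes leaving the suite, so elimination again points to the axillary sensor.

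**3. Scale, from the protocol's own figures**

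- Required fall: 36.8 − 35.5 = 1.3°C to 37.5 − 35.5 = 2.0°C.
- Mean rate if the full 2 hours are used: 1.3/2 = 0.65°C/h to 2.0/2 = 1.0°C/h.
- Entry window: 37.5 − 36.8 = 0.7°C.

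The documents give no between-sensor offset. For an **assumed** offset d, in either direction, its share of the fall runs from d/2.0 to d/1.3, its share of the entry window is d/0.7, and its effect on a 2-hour rate is d/2:

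| Assumed d (°C) | Share of required fall | Share of entry window | Shift in 2-hour rate (°C/h) |
|---|---|---|---|
| 0.1 | 5.0–7.7% | 14.3% | 0.05 |
| 0.3 | 15.0–23.1% | 42.9% | 0.15 |
| 0.5 | 25.0–38.5% | 71.4% | 0.25 |

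The shares of the fall and the rate shifts apply only if baseline and target come from different sensors. The minute at which the in-scanner sensor first shows 35.5°C does not depend on which baseline sensor is used.

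**The case against.** The best defence is that the conflict has only one practical resolution. With one sensor left, *either* means that sensor, and section 4.1 independently states the 35.5°C target next to a single MRI compatible thermometer. This stands. A reader might infer that the rule cannot be carried out, or that staff would time the target in different ways and so bias the count. The documents do not support that: no second sensor is available during cooling to produce a different answer.

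A reader might also infer that the protocol applies the term core to different sensors in its two closing branches. One branch follows the participant's "core body temperature until it returns to baseline" and then removes the axillary thermometer; the other does so after the forehead and tympanic readings outside the suite. That inference rests on line order alone. Neither monitoring step names a sensor, and nothing says the axillary sensor is abandoned in the second branch.

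It is further argued that the fall and the cooling rate are not listed endpoints, that an axillary baseline and a pre-cooling reading are both collected, and that the choice of baseline is often left to the analysis plan, which is not at hand. This stands in part. A same-sensor baseline exists, and mixing sensors is possible rather than prescribed. But the entry range is applied at the bedside, where a later analysis plan cannot settle it, and the conflict between 7.5 and 7.6.3 lies within the protocol itself.

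Finally, the offsets in the table are assumed. They illustrate scale and cannot support a claim about size.

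**Conclusion.** The contradiction is established from the text: two sensors are required during cooling and one remains. Its consequence is limited but real. On the current wording, all three primary endpoints rest by elimination on an axillary reading that no section designates as core. The sensor for entry and for baseline is left open, so baseline and target may be on different measurement scales.

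No bias in the number reaching 35.5°C is shown. The only quantified consequence is conditional: if the sensors differ by an assumed 0.1–0.5°C, that is 5–38% of the required fall, 14–71% of the entry window and 0.05–0.25°C/h on a 2-hour rate. The sensor count assumes that the removal step in 7.5 is followed and that cooling takes place in the scanner suite, as 4.1 describes. This should be corrected, because it determines what the trial may say it measured. It does not invalidate the primary count.

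**What to change.** 1. Reconcile sections 4.1, 7.5 and 7.6.3, including the second, apparently misplaced instruction to remove the forehead and tympanic sensors.
2. Replace *both* and *either* with one named sensor that is present throughout cooling. On the current text only the axillary sensor qualifies. State in 5.1 and 12.1 that it is used for reaching 35.5°C, for the one-hour maintenance endpoint and for the body side of the gradient.
3. Take baseline from that same sensor at a named time point, either the 7.5 reading or the pre-cooling reading in 7.6.3.
4. State which sensor sets eligibility in the Synopsis and 6.1.
5. Label results by measurement site rather than as core temperature.
6. Optionally, tabulate the baseline forehead-minus-axillary and tympanic-minus-axillary differences. The readings are already collected, and the table would replace the assumed offsets above with observed ones.

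The bedside steps that use the same undefined reading (ending induction, responding to low temperature, adjusting flow during maintenance, following the return to baseline) must be reconciled by the sponsor. No clinical rule is proposed here.

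The cost is protocol wording and, if wanted, one descriptive table. The downside for the sponsor is that a result labelled by measurement site is a less favourable claim than one labelled core temperature.
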